7.9.3.4. Other Analyses of the Open-Label Period

Additional descriptive analyses of the OLE data will include (1) an extension of the primary analysis NCS model respecting the blinded-phase randomized group assignments; and (2) an extension of the exposure adjusted model (Section 7.9.1.2.4).

7.10. Analyses of Cogstate/C3 Outcome Measures

The cognitive tests administered in the study include the following computerized tests from the Cogstate Battery. Each of these tests has been described in detail in the literature and hence they are described only briefly below. The order of administration is reflected in the order in which each test is described.

Detection (DET; Psychomotor Function)

The Detection test is a measure of psychomotor function and uses a well-validated simple reaction time paradigm with playing card stimuli. In this test, the playing cards all depict the same joker. The subject is asked to press the **Yes** key as soon as the card in the center of the screen turns face up. The software records the number of correct responses and expresses the number of correct responses as a proportion of the trials completed (accuracy). Data distributions for this proportion correct score are normalized using an arcsine transformation (asin prop correct). The software also records the speed of reaction times (RT) for correct responses in milliseconds (msec). Distributions of RT are then normalized through application of a logarithmic base 10 ($\log_{10}RT$) transformation.

Identification (IDN; Attention)

The Identification test is a measure of visual attention and uses a well-validated choice reaction time paradigm with playing card stimuli. In this test, the playing cards are all either red or black jokers. The subject is asked whether the card displayed in the center of the screen is red. The subject responds by pressing the **Yes** key when the joker card is red and **No** when it is black. The software records the number of correct responses and speed of reaction times for correct responses and expresses these as accuracy (asin prop correct) and speed ($\log_{10}RT$).

One Card Learning (OCL; Visual Learning)

The One Card Learning test is a measure of visual learning and uses a well-validated pattern separation paradigm with playing card stimuli. In this test, the playing cards are identical to those found in a standard deck of 52 playing cards (without the joker cards). The subject is asked whether the card displayed in the center of the screen was seen previously in this test. The subject responds by pressing the **Yes** or **No** key. The software records the number of correct responses and speed of reaction times for correct responses and expresses these as accuracy (asin prop correct) and speed ($\log_{10}RT$).

One Back (ONB; Working Memory)

The One Back test is a measure of working memory and uses a well-validated n-back paradigm with playing card stimuli. In this test, the playing cards are identical to those found in a standard deck of 52 playing cards (without the joker cards). The subject is asked whether the card displayed in the center of the screen is the same as the card presented immediately previously. The subject responds by pressing the **Yes** or **No** key. Because no card has been presented yet on the first trial, a correct first response is always **No**. The software records the number of correct responses and speed of reaction times for correct responses and expresses these as accuracy (asin proportion correct) and speed ($\log_{10}RT$).

Behavioral Pattern Separation Object Test (BPSO; Recognition Memory)

The Behavioral Pattern Separation Object (BPSO) test is a measure of recognition memory. The BPSO test is divided into two sub-tests: 1) "Indoor-Outdoor" (BPET) and 2) "Old, Similar, New" (BPXT). This first test presents a series of photos of common objects to the subject who is asked to decide whether each object is primarily used indoors or outdoors. Once the "Indoor-Outdoor" test (BPET) has been completed, the "Old, Similar, New" test (BPXT) will begin. A series of images of common objects will be presented to the subject who is asked to decide if the object is the same as one they saw before, similar to one they saw before, or an entirely new object altogether. The software computes a BPSO metric, which is calculated as the difference of the probability of a "Similar" response to a "Similar" image and the probability of a "Similar" response to a "New" image (Stark et al. 2013). The probability of a 'Similar' response to a 'Similar' image is compute by summing the 'Similar' responses to a 'distractor' stimulus, divided by the sum of total responses to a 'distractor' stimulus. The probability of a "Similar" response to a "New" image is computed by summing the total number of 'Similar' responses when the stimulus was a 'New' item and dividing it by the sum of the total responses to a 'New'

item. The other outcome calculated for this test is the ‘percentage correct’ for ‘Old’ and ‘New’ responses. The probability of a response to an ‘Old’ item and the probability of response to a ‘New’ item are summed and divided by 2, to compute the percentage correct outcome. These outcomes are described in Stark et al.,

Face Name Associative Memory Exam (FNAME; Associative Memory)

The Face Name Associative Memory Exam is a measure of associative memory using visual stimuli. The subject is shown a series of faces and names, and is asked to remember the face-name pair. Each face is then presented again, and the subject must recall and input the name that was associated with that face. The correct number of face-name pairs is recorded as an initial learning score. After a delay the subject is shown each face again, along with three names listed underneath it. The subject must select the name that was initially paired with the face. The software records the number of correct responses and speed of reaction times for correct responses and expresses these as accuracy (asin prop correct) and speed ($\log_{10}RT$).

For each Cogstate computerized cognitive test, a single primary outcome measure was selected prior to data analysis from each test in the battery to minimize experiment-wise error rates. Each primary outcome measure was selected because it has been shown to be optimal for the detection of change.

A supporting document created by Cogstate, also called a statistical analysis plan, but limited to aspects related to the Cogstate battery, will be filed with the study documents. It contains further technical details and references related to the Cogstate battery.

The main outcome from the computerized test battery will be the C3 composite.

- C3 Composite Score (6 items): BPSO, FNAME (matching), DET, IDN, OCL, ONB (speed): computed only if z-scores are available for a minimum of four tests.

Exploratory composite outcomes will include the composite

- Learning/Working Memory Composite: OCL and ONB (accuracy): computed only if z-scores are available for both tests
- One Card Learning/One back speed accuracy composite: OCL and ONB (speed and accuracy): computed only if z-scores are available for both tests
- Psychomotor/Attention Composite: DET and IDN: computed only if z-scores are available for both tests
- Attention Domain Composite: DET, IDN, and ONB (speed): computed only if z-scores are available for all three tests
- C3 Composite Score (3 items) – Abbreviated: BPSO, FNAME (matching), OCL: computed only if z-scores are available for all three tests

7.11. Analyses of Resource Utilization Data

Resource utilization as measured by Resource Use Inventory, Brief version (RUI-B) will be compared across treatment groups in the placebo-controlled period. Continuous data will be analyzed using an NCS model and categorical data will be analyzed using Fisher's exact test.

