10.1.2.5. Resource Use Inventory—Brief Version

The Resource Use Inventory (RUI) is an instrument designed to assess changes associated with the transition from normal aging to dementia in (1) health-related resource use (medical care, nonmedical care, and informal care) and (2) elders' participation in volunteer and paid work. Medical care includes questions on hospitalization, outpatient treatment and procedures, assistive devices, and medications. Nonmedical care includes questions on home health aides, respite care, and adult day care. Informal caregiving time participants received with instrumental and basic ADL. Both participants and their study partners contribute to the reporting of the RUI to maximize information obtained. The RUI has been used in trials of normal aging (Sano et al. 2006), MCI (Zhu et al. 2013), and dementia (Zhu et al. 2006), and items are included that are relevant to the specific stage of cognitive impairment and dementia. For this trial, a brief version of the inventory will be used (the RUI-B, where B stands for brief), including only those items

that are relevant to this stage with a focus on volunteer and paid work and items for medical and nonmedical resources.

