5.3. Exploratory Objectives

The exploratory objectives of the study are as follows:

- To assess the effect of treatment with solanezumab as demonstrated using the MMSE.
- To assess the utility of a novel computerized battery, the Computerized Cognitive Composite (C3), in predicting and tracking clinical decline and response to solanezumab.
- To assess the effects of treatment on healthcare resource utilization.
- To determine the best predictors of clinical decline based on the PACC.
- To develop novel sensitive outcome measures to improve the efficiency of future secondary prevention trials, including exploratory measures of self-reported assessment of cognitive and interpersonal functioning.
- To assess the effect of treatment with solanezumab as demonstrated using the Clinical Dementia Rating (CDR) scale.
- To assess the effect of treatment with solanezumab as demonstrated using the C-Path Consortium’s Participant-Reported Outcome Questionnaire (C-Path PRO).
- To investigate the impact of solanezumab on markers of synaptic dysfunction on functional connectivity MRI.
- To test the hypothesis that solanezumab reduces brain tau burden, as compared with placebo, as assessed using flortaucipir positron emission tomography (PET) imaging.

- To assess solanezumab-associated changes in levels of plasma A β species and CSF A β species. The hypothesis that solanezumab, unlike placebo, alters amyloid-plaque associated forms of A β will be assessed by 1) demonstrating presence of plaque-associated A β species in the plasma, and 2) confirming that concentrations of CSF free (unbound to antibody) A β_{1-42} are increased or unchanged and CSF free A β_{1-40} levels are decreased with solanezumab treatment.
- To explore whether baseline markers of neurodegeneration (volumetric MRI or CSF tau or p-tau) are related to cognitive decline and response to treatment with solanezumab.
- To explore the impact of disclosure of amyloid status on questionnaires probing perception of amyloid imaging and concern about developing AD.
- To explore biomarker assessments collected at baseline and at the end of the placebo-controlled period as potential predictors of treatment effect during the open-label period.

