6.1. Summary of Study Design

Study A4 is a multicenter, randomized, double-blind, placebo-controlled, Phase 3 study comparing solanezumab with placebo for 240 weeks in approximately 1150 participants ages 65 to 85 years old with preclinical AD, defined as having evidence of brain amyloid pathology without clinically evident cognitive impairment at screening. Participants who met entry criteria were randomized in a 1:1 ratio (approximately 575 per treatment arm) to solanezumab or placebo once every 4 weeks. Participants were randomized within the site by education – high (13 or more years) or low (12 or less years) and the presence of one or more apolipoprotein E gene (APOE) ϵ 4 alleles (yes, no). The primary hypothesis being tested is that the cognitive decline at the end of the placebo-controlled period will be significantly less for solanezumab than for placebo. Participants completing the placebo-controlled period of the study can opt to participate in the open-label period of the study that will last for up to 204 weeks or until the primary analyses of the placebo-controlled period of the study are completed and reviewed.

At the beginning of the COVID-19 pandemic, a hiatus was implemented to allow participants to pause study activities without missing visits and resume when COVID safety mitigations were in place (for example, vaccines, home infusions, etc.). The hiatus extended the end of the placebo-controlled period for up to 9 months and the placebo-controlled period will be administratively closed in December 2022.

Figure A4.SAP.1 illustrates the study design.

Abbreviation: V = visit.

Figure A4.SAP.1. Illustration of study design for Clinical Protocol A4.

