6.2. Determination of Sample Size

In order to develop an appropriate measure of cognitive decline in a preclinical population, we tested several combinations of measures using data from longitudinal studies in clinically normal populations, including the ADNI; the AIBL; the ADCS-PI trial; and the HABS.

Sample size and power at 4.5 years (240 weeks) for the PACC were estimated using data from ADNI and HABS. Estimates were obtained by applying appropriate assumptions regarding treatment difference, SD, and attrition for a 4.5-year study in a preclinical AD population. In ADNI, the difference in the composite change between participants with and without elevated brain amyloid at 240 weeks was 2.13 (SD=2.85). Similarly, in HABS, the difference in the composite change between participants with and without elevated brain amyloid at 240 weeks was 2.66 (SD=3.08). Given the ADNI-derived estimate of SD at 240 weeks of SD=2.85 and 30% attrition, the total N=1150 provides 80% power (5% 2-sided alpha) to detect a treatment difference of 0.532 points or $0.532/2.13 = 24.9\%$ of the amyloid group difference. Similarly, based on the HABS estimate of SD at 240 weeks of SD=3.08, the study has 80% power to detect a treatment difference of 0.570 points or $0.570/2.66 = 21.4\%$ of the amyloid group difference.

For the open-label period, the estimated mean PACC difference between cognitively normal participants with and without elevated brain amyloid at 336 weeks is 2.95 (SD=3.77) based on ADNI and 4.74 (SD=3.99) based on HABS. Accounting for the administrative censoring that will be induced by the common close design of the open-label period, and assuming an overall attrition rate of 30%, about 266 PACCs are expected to be available at 336 weeks. The visit-to-visit correlation is estimated to be about 0.5. Under these pilot estimates, 266 PACCs at 336 weeks would provide 80% power to detect a randomized group (early-start vs delayed-start treatment with solanezumab) difference of about 0.9 PACC points. This change of 0.9 PACC points reflects 30% of the difference between amyloid-positive and -negative participants based on ADNI, and 20% of that difference based on HABS.

Sample size for the study was determined assuming an MMRM analysis prior to the interruption caused by the COVID-19 pandemic. Applying the NCS approach in simulated trials with a COVID-19 pandemic interruption suggests the study has 94% power to detect an effect size of 0.75 PACC points at 240 weeks.

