7.1. General Considerations

Unless otherwise noted, all tests of treatment effects will be conducted at a 2-sided alpha level of 0.05; 2-sided confidence intervals will be displayed with a 95% confidence level. All tests of interactions between treatment and other factors will be conducted at an alpha level of 0.05.

All analyses will follow the modified intent-to-treat (mITT) principle unless otherwise specified. An ITT analysis is an analysis of data by groups to which the participants are assigned by random allocation, even if the participant does not take the assigned treatment, does not receive the correct treatment, or otherwise does not follow the protocol. An mITT analysis is an ITT analysis for all participants who have a baseline and at least 1 postbaseline measure. All safety analyses will be done using the safety population. Analysis populations are described below (Section 7.5).

When change from baseline is assessed, participants will be included in the analysis only if both a baseline and a post-baseline measure are available. Unless otherwise defined, a baseline measure is the last non-missing observation collected prior to the first infusion of study medication. End point is the last non-missing post-baseline measurement.

For MMRM analyses, observations collected at non-scheduled visits (see Section 7.2) will not be included in the analyses. For NCS and MMRM analyses, unless otherwise specified, an unstructured covariance structure will be used. If the unstructured covariance structure matrix results in a lack of convergence, the following covariance structures will be used in sequence: heterogeneous Toeplitz covariance structure, heterogeneous autoregressive covariance structure, heterogeneous compound symmetry covariance structure and homogeneous compound symmetry covariance structure.

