7.6. Participant Characteristics

Baseline characteristics will be summarized for the ITT and per-protocol populations by treatment group and overall. Summaries will include descriptive statistics for continuous and categorical measures. Fisher's exact test or Pearson's chi-square test will be used for treatment-group comparisons of categorical data. For continuous data, analysis of variance (ANOVA), with independent factor for treatment will be used. Participant characteristics to be presented include:

- age
- gender
- race
- height
- body weight
- body mass index (weight (kg) / [height (m)]²)
- tobacco use
- alcohol use
- caffeine use

- years of education
- work status
- Baseline score as measured by PACC, ADL Prevention Questionnaire, CFI, CDR-SB, C3, MMSE, RUI-B.
- APOE4 carrier status (carrier [$\epsilon 2/\epsilon 4$, $\epsilon 3/\epsilon 4$, $\epsilon 4/\epsilon 4$], noncarrier [$\epsilon 3/\epsilon 3$, $\epsilon 2/\epsilon 2$, $\epsilon 3/\epsilon 2$]), and
- APOE4 genotype ($\epsilon 2/\epsilon 4$, $\epsilon 3/\epsilon 4$, $\epsilon 4/\epsilon 4$, no $\epsilon 4$), and
- Baseline Amyloid Centiloids

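### SAP 7.11 compares categorical RUI-B items without using their baseline answers: a valid test on an exploratory outcome, but one that gives up precision for items that persist

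*SAP*

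**What the plan says.** SAP 7.11 covers the placebo-controlled comparison of RUI-B in two sentences. The operative one is "Continuous data will be analyzed using an NCS model and categorical data will be analyzed using Fisher's exact test". For the categorical part it names no baseline value, covariate, stratum or visit.

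Baseline RUI-B data exist. The placebo-controlled schedule in Protocol Attachment 1 marks RUI-B at Visit 6 and at Weeks 48, 108, 168 and 240. SAP 7.6 includes it among the baseline characteristics to be presented: "Baseline score as measured by PACC, ADL Prevention Questionnaire, CFI, CDR-SB, C3, MMSE, RUI-B". Protocol 10.1.2.5 describes the content of the brief version as limited to items relevant at this stage, "with a focus on volunteer and paid work and items for medical and nonmedical resources".

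The outcome's status is clear. SAP 5.3 lists "To assess the effects of treatment on healthcare resource utilization" among the exploratory objectives, and SAP 7.4 places everything except the NCS analysis of the PACC outside the primary test. No power is stated for resource use.

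**The concern.** Within one sentence the plan treats two kinds of data from the same instrument differently. SAP 7.11 does not write out the NCS model for continuous RUI-B data. If it follows SAP 7.9.1.1, the baseline score is part of the outcome vector and covariates are included. The categorical items get neither.

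The rest of the SAP generally uses baseline where it is informative. The MMRM for additional clinical outcomes (7.9.2.1) and the ANCOVA models for florbetapir, plasma, volumetric MRI and CSF (7.12) all carry the baseline value. The nearest parallel is CDR Global Score (7.9.2.2), where Fisher's test is also planned. There, every participant starts at 0, so no baseline information is lost, and an adjusted Cox model is added. RUI-B answers can differ between participants at entry, yet no adjusted analysis is given.

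If a person's answer at Week 240 depends on the answer at entry, part of the between-person variation is already known and could be removed at no data cost. What is at stake is the chance of detecting a real difference on an exploratory item.

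**Working it through.** **The plan's own figure.** There is none for RUI-B. Prevalence, difference and persistence below are therefore assumptions.

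**Inputs from the documents**
- Two-sided alpha of 0.05: SAP 7.1, "all tests of treatment effects will be conducted at a 2-sided alpha level of 0.05".
- About 575 per arm: SAP 6.1.
- Attrition: SAP 6.2, "30% attrition, the total N=1150 provides 80% power (5% 2-sided alpha) to detect a treatment difference of 0.532 points". Removing 30% gives 575 × 0.70 = 402.5, so about 402 per arm at Week 240.

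**Assumed inputs**
- Control rates of 15 to 40% and differences of 6 to 10 points.
- Phi, the correlation between a person's yes/no answers at baseline and Week 240, of 0.2 to 0.6.
- A two-category item compared at Week 240, since SAP 7.11 names neither visit nor table.

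**Step 1: hand calculation, 30% v 38%, 402 per arm.** For the ordinary two-proportion test:
- pooled rate 0.34; SE under the null = √(2 × 0.34 × 0.66 / 402) = 0.0334
- SE under the alternative = √((0.30 × 0.70 + 0.38 × 0.62) / 402) = 0.0333
- power = Φ((0.08 − 1.96 × 0.0334) / 0.0333) = Φ(0.436) = 66.9%

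Fisher's test in simulation gives 63 to 65% for the same setting.

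Adjusting for baseline multiplies the variance by about (1 − phi²), so power becomes approximately Φ(2.396 / √(1 − phi²) − 1.96), where 2.396 = 0.436 + 1.96:
- phi 0.2: 2.396 / 0.980 = 2.445, power 69%
- phi 0.3: 2.396 / 0.954 = 2.512, power 71%
- phi 0.4: 2.396 / 0.917 = 2.614, power 74%
- phi 0.5: 2.396 / 0.866 = 2.766, power 79%
- phi 0.6: 2.396 / 0.800 = 2.995, power 85%

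Simulated CMH power, stratified by the baseline answer, is 74%, 79% and 86% at phi 0.4, 0.5 and 0.6, which agrees.

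**Step 2: simulation.** 6,000 trials per setting. The gain is CMH power minus Fisher power, in percentage points.

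| Rates, n per arm | Fisher power | phi 0.2 | 0.3 | 0.4 | 0.5 | 0.6 |
|---|---|---|---|---|---|---|
| 15% v 22%, 402 | 68–70% | 4.9 | 8.1 | 11.1 | 16.4 | 21.8 |
| 20% v 28%, 402 | 72–74% | 4.0 | 7.2 | 9.9 | 14.2 | 19.9 |
| 30% v 36%, 402 | 40–43% | 4.5 | 5.9 | 9.8 | 15.5 | 20.5 |
| 40% v 50%, 402 | 79–80% | 3.1 | 5.4 | 7.8 | 11.4 | 14.9 |
| 30% v 40%, 575 | about 94% | 1.4 | 2.6 | 3.7 | 4.6 | 5.0 |

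At phi 0.7 the gain at 402 per arm reaches about 32 points (30% v 36%).

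**Step 3: a logistic model does the same job.** With the baseline answer as covariate, 402 per arm and 1,500 trials per setting:
- 35% v 42%, phi 0.6: Fisher 49%, logistic 71%
- 35% v 42%, phi 0.5: Fisher 51%, logistic 68%
- 25% v 31%, phi 0.4: Fisher 46%, logistic 54%

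**Step 4: how much is Fisher's conservatism?** Under no effect (20,000 trials), Fisher rejected in 4.0 to 4.2% and CMH in 4.9 to 5.1%. The unadjusted Pearson test exceeded Fisher by 1.8 to 3.2 points in the 402-per-arm rows above, and by under 1 point in the 575 row. At phi 0.2 this is more than half of the gain (15% v 22%: 3.2 of 4.9 points).

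**The case against.** The strongest reply is that nothing here is an error. Fisher's exact test holds its level, it is the SAP's standard choice for categorical comparisons, and resource use is exploratory and unpowered. All of that stands. A reader might infer a biased or invalid test, or a threat to the trial's main conclusion; the documents support neither.

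A second reply is that the size has no source. This also stands. A reader might take 8 to 22 points as an established loss, but it follows only from an assumed phi of 0.4 to 0.6 at about 402 per arm. Nor should it be spread over every item. The instrument covers medical and nonmedical resources as well as work, and no document shows that service use persists over 240 weeks. Such items may lie at the low end, where the gain is a few points and much of it is Fisher's conservatism.

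Third, it would be over-reading to say that SAP 7.11 plans a two-by-two table at Week 240. It names no visit, and the categorical variable could be status at each visit, at any time, or a change category. That is a reason to name the visit in the repair.

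Finally, one might want a repeated-measures model across all visits, such as GEE. No power was calculated for it. Unweighted GEE generally needs a stronger missing-data assumption than missing at random, which is unattractive with 30% attrition. It would also tie the analysis to visit, when the SAP adds continuous-time biomarker analyses because COVID separated visit from time. It is not needed.

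What survives all four is the direction: every scenario checked showed a gain, and the baseline data are already collected.

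**Conclusion.** The point holds as a free improvement of minor weight. The planned comparison is valid but inefficient for categorical RUI-B items that persist from entry.

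Under the stated assumptions (about 402 per arm, unadjusted power of roughly 40 to 83%), baseline adjustment gains about 3 to 8 points of power at phi 0.2 to 0.3 and about 8 to 22 points at phi 0.4 to 0.6. About 1 to 3 of those points come from leaving Fisher's conservative test. Where unadjusted power is already about 94%, the gain is about 1 to 5 points over the same range of phi. The documents do not settle which of these cases applies to any given item.

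**What to change.** In SAP 7.11, for each binary RUI-B item at Week 240, replace Fisher's exact test with one of two analyses:
- a logistic model with treatment, the baseline response to the same item, age, education and APOE4 carrier status; or
- a CMH test stratified by the baseline response.

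Report the adjusted risk difference with its 95% confidence interval, since the odds ratio from an adjusted logistic model is conditional on the covariates. Keep Fisher's exact test for items too sparse to fit, under a rule written down in advance. State the visit explicitly and say how items with more than two categories are handled.

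The cost is a few lines of SAP text, minor programming and the sparse-item rule. No new data are needed. Protocol 11.2.1 requires an amendment only when a principal feature changes, which this does not. The change should be made before unblinded analysis; if made later, the adjusted result should be labelled post hoc.
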